**Cohort C (Ewing/Ewing-like sarcoma):**

Since progression free survival is so short in Ewing/Ewing-like sarcoma, even with an active agent such as an IGF1R inhibitor (1.3 months in one study), a single-stage design examining PFS at 8 and 16 weeks will be employed for this cohort.

We will take median PFS of 0.5 at 8 weeks as evidence of activity for this cohort, in comparison to an uninteresting median PFS (8 weeks) of 0.25. For this 30 patient cohort with these parameters, this yields a false positive rate of 0.05 (alpha) and power (1-beta) of 0.91.

The response rate will be estimated and a confidence interval will be constructed. A sample size of 30 patients and 50% PFS rate at 8 weeks yields a 95% binomial confidence interval of (31%, 69%).

**Cohort D (Rhabdomyosarcoma: Fusion-positive alveolar, Embryonal, Fusion-negative alveolar):**

Since published estimates of progression free survival in rhabdomyosarcoma patients after more than one relapse are scarce, we will estimate the RECIST 1.1 Response rate (PR or better) at 8 weeks. Cohort D will accrue separately to approximately 12 patients with either of (1) fusion-positive alveolar rhabdomyosarcoma and (2) embryonal rhabdomyosarcoma/fusion negative alveolar rhabdomyosarcoma, and will be analyzed as a combined cohort. We will consider a disease control rate (CR+PR+stable disease at 8 weeks) of 30% to be evidence of activity, in comparison to a disease control rate of 10% as not useful to pursue further.

A total of ~ 12 patients will be accrued to Cohort D and ~ 12 to Cohort E, below. Since funding is available for 24 patients in Cohorts D and E, the below are estimates of accruals, and the actual accrual will be used to define success vs failure for each cohort based on final accrual, maintaining similar disease control rates at 8 weeks (30% [active] vs 10% [not active]) for Cohort D, regardless of final accrual total.

For a 12-patient cohort with a type I error of 0.10 and a power of 0.90, if 2 or fewer patients have disease control, then regorafenib will be determined to be unworthy of further study in this setting. If 3 or more patients have disease controlled at 8 weeks, regorafenib will be considered worthy of further investigation in Cohort D. A sample size of 12 patients will permit determination of disease control rate of 30% with 95% binomial confidence interval of (10%, 57%).

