### **Maximum Total Number of Subjects**

Cohort A: 48, seeking 42 events in 16 months

Cohort B: 48, seeking 42 events in 16 months

Cohort C: Single stage phase II design, n=30

Cohort D: Single stage phase II design, n ~ 12\*

Cohort E: Single stage phase II design, n ~ 12\*

\*These two arms will enroll a total of 24 patients, given the study funding for 24 patients. The number of people studied in each group will vary according to the ability to accrue either diagnosis.

Number of enrolling centers: approximately 18

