### **Cohort E (Mesenchymal chondrosarcoma):**

Published estimates of progression free survival on chemotherapy for patients with metastatic mesenchymal chondrosarcoma patients are also unavailable. However, existing data indicate the overall survival of patients with metastatic mesenchymal chondrosarcoma is similar to those with unselected soft tissue sarcomas, in the 18 month range (Amer et al. J Orthop Res 2019, <https://doi.org/10.1002/jor.24463>), so we will estimate the RECIST 1.1 response rate (PR or better) at 24 weeks. Cohort E will accrue to ~ 12 patients with metastatic mesenchymal chondrosarcoma. We will consider a disease control rate (CR+PR+stable disease) at 24 weeks of 50% to be evidence of activity, as is the case with 1st line doxorubicin or gemcitabine in unselected STS (GEDDiS study) in comparison to a disease control rate of 25%, as not useful to pursue further.

A total of ~ 12 patients will be accrued to Cohort E,. Since funding is available for 24 patients in Cohorts D and E, the estimates of accruals, and the actual accrual will be used to define success vs failure for each cohort based on final accrual, maintaining similar disease control rates at 24 weeks (50% [active] vs 25% [not active]) for Cohort E, regardless of final accrual total.

The design is based on a Simon's two-stage using only the first stage. A 12-patient cohort with a type I error of 0.10 and a power of 0.80, yields a decision rule that if 3 or fewer patients have disease control at 24 weeks, then regorafenib will be determined to be unworthy of further study in this setting. If 4 or more patients have disease controlled at 24 weeks, regorafenib will be considered a worthy of further investigation in Cohort E. A sample size of 12 patients will permit determination of 24-week disease control rate of 50% with 95% binomial confidence interval of (21%, 79%).

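### Cohorts D and E have a success cut-off only for 12 patients; at any other size the plan names neither the error criterion that sets it nor when it is fixed

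*Combined protocol and SAP*

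**What the plan says.** Combined protocol and SAP, section 12.2, sets these rules:

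- **Cohort D** (8-week disease control, 10% versus 30%): "For a 12-patient cohort with a type I error of 0.10 and a power of 0.90". Success is defined by "If 3 or more patients have disease controlled at 8 weeks".
- **Cohort E** (24-week disease control, 25% versus 50%): "A 12-patient cohort with a type I error of 0.10 and a power of 0.80". Success is defined by "If 4 or more patients have disease controlled at 24 weeks". The rule is described as the first stage of a Simon two-stage design.

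Both cohort descriptions then say that "the actual accrual will be used to define success vs failure for each cohort based on final accrual". What stays fixed is the pair of rates: "maintaining similar disease control rates at 8 weeks (30% [active] vs 10% [not active]) for Cohort D, regardless of final accrual total", and for E "maintaining similar disease control rates at 24 weeks (50% [active] vs 25% [not active]) for Cohort E, regardless of final accrual total".

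The Synopsis (Maximum Total Number of Subjects) fixes only the joint total of 24 and adds: "The number of people studied in each group will vary according to the ability to accrue either diagnosis". Section 5.1 and the Brief Statistical Design make both cohorts single-arm, with every patient on regorafenib. Section 12.3 expects 0.5 patients per month in each. No section gives a formula, a table of cut-offs, an error limit for other sizes, or a date by which the cut-off must be set.

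**The concern.** A null rate and a target rate do not determine a cut-off. A criterion is also needed: hold type I error, hold power, or keep the 12-patient proportion. The plan expects sizes other than 12 but names no criterion for them. If the candidate criteria give different cut-offs, an observed count lying between them is a success or a failure according to a choice the plan leaves open. These cohorts are not blinded, and final size is known late, so that choice could be made by people who have seen the responses. At stake is the go/no-go conclusion for the two cohorts that section 3.1 does not mark as closed to enrolment.

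**Working it through.** **Inputs.** Rates p0/p1 are 0.10/0.30 (D) and 0.25/0.50 (E). Stated alpha/power are 0.10/0.90 (D) and 0.10/0.80 (E). All come from section 12.2. Sidedness is not stated; the rules use the upper tail, so alpha is taken as one-sided.

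**Formula.** For n patients and success at r or more, alpha = 1 − Σ(k<r) C(n,k) p0^k (1−p0)^(n−k). Power is the same expression with p1.

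**Step 1: the plan's own rules at n = 12.**

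- D, r = 3: alpha = 1 − (0.2824 + 0.3766 + 0.2301) = 0.111; power = 1 − (0.0138 + 0.0712 + 0.1678) = 0.747. Stated: 0.10/0.90.
- E, r = 4: alpha = 1 − (0.0317 + 0.1267 + 0.2323 + 0.2581) = 0.351; power = 1 − (0.0002 + 0.0029 + 0.0161 + 0.0537) = 0.927. Stated: 0.10/0.80.

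Neither pair reproduces, and neighbouring cut-offs do not help: D gives 0.341/0.915 at 2 and 0.026/0.507 at 4; E gives 0.158/0.806 at 5 and 0.054/0.613 at 6. For E, 3 or fewer of 12 can be the stage-1 futility bound of a full Simon design (for example 3/12 then 7/19: 0.074/0.807), but those errors belong to both stages together. The printed rules therefore cannot show which criterion to carry to another n.

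**Step 2: n = 16.** The total of 24 allows 16 in one cohort and 8 in the other.

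- D, r = 3: alpha = 1 − (0.1853 + 0.3294 + 0.2745) = 0.211; power = 1 − (0.0033 + 0.0228 + 0.0732) = 0.901.
- D, r = 4: subtract P(X = 3), which is 0.1423 under p0 and 0.1465 under p1, giving 0.068/0.754.
- E, r = 6: alpha = 1 − (0.0100 + 0.0535 + 0.1336 + 0.2079 + 0.2252 + 0.1802) = 0.190; power = 1 − (0.0000 + 0.0002 + 0.0018 + 0.0085 + 0.0278 + 0.0667) = 0.895.
- E, r = 7: subtract P(X = 6), which is 0.1101 under p0 and 0.1222 under p1, giving 0.080/0.773.

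**Step 3: cut-offs by criterion (alpha/power in brackets).**

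| Cohort, n | Smallest r with alpha ≤ 0.10 | Largest r with stated power | Same proportion as at n = 12, rounded up |
|---|---|---|---|
| D, 8 | 3 (0.038/0.448) | 1 (0.570/0.942) | 2 (0.187/0.745) |
| D, 14 | 4 (0.044/0.645) | 2 (0.415/0.953) | 4 (0.044/0.645) |
| D, 16 | 4 (0.068/0.754) | 3 (0.211/0.901) | 4 (0.068/0.754) |
| E, 8 | 5 (0.027/0.363) | 3 (0.321/0.855) | 3 (0.321/0.855) |
| E, 10 | 5 (0.078/0.623) | 4 (0.224/0.828) | 4 (0.224/0.828) |
| E, 14 | 7 (0.038/0.605) | 5 (0.258/0.910) | 5 (0.258/0.910) |
| E, 16 | 7 (0.080/0.773) | 6 (0.190/0.895) | 6 (0.190/0.895) |

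So 3 of 16 in D and 6 of 16 in E each pass on stated power and fail on stated alpha.

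**Step 4: can both errors be met?** For D the smallest n is 25 (r = 5: 0.098/0.910), more than the 24 funded for both cohorts. For E the smallest is 19 (r = 8: 0.077/0.820); 21 to 23 with r = 9 also work. Near 12 neither cohort has such a cut-off.

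**Step 5: timing.** Assume even accrual, one patient every 2 months, so the 12th enrols at month 22. Eight weeks is 8 × 7/30.4 = 1.8 months, so D patients enrolled by month 20 (11 of 12) have passed the landmark. Twenty-four weeks is 5.5 months, so E patients enrolled by month 16 (9 of 12) have passed theirs.

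**The case against.** The fairest defence is that the plan does have a rule in outline. Both rates are fixed whatever the final size, and alpha and power are stated in the paragraph that follows, so the intention may be to rerun the same calculation at the actual n. That stands in part: it would be wrong to say that nothing is specified. But the rerun has no solution at any possible size in D, or near 12 in E, until one of the two errors is given priority, and the plan does not do that.

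A reader might infer that the cut-off will be chosen after outcomes are known. The documents do not say so; they give no timing at all. What can be said is that final size emerges late and nothing shields whoever sets the cut-off.

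A reader might also infer that the problem vanishes if each cohort lands on exactly 12. It does not, because the printed 12-patient rules miss their stated errors, most clearly in E. Nor is it true that no size satisfies the stated pair: E does at 19.

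Finally, the stakes are bounded. The primary objectives in section 1.1 are to estimate rates in D and E, and the observed proportion and its interval can be read without any cut-off.

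**Conclusion.** The concern holds in this form: away from 12 patients, section 12.2 fixes the two rates but neither the governing error criterion nor the time at which the cut-off is set. Near 12 the choice of criterion moves the cut-off by one or more patients, enough to reverse the conclusion on counts such as 3 of 16 (D) or 6 of 16 (E). In those two examples alpha moves from 0.068 to 0.211 and from 0.080 to 0.190. The 12-patient rules give no sound anchor.

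The result rests on exact one-sided binomial tails at the plan's own rates. The remark on outcomes being in view is an inference that also assumes even accrual at the stated pace. The documents support a gap that allows a data-dependent choice, not a finding that one is intended. The change should be made, but it bears on a go/no-go reading in small single-arm cohorts, not on the randomised comparisons.

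**What to change.** Before any outcome review, add to section 12.2 a table of cut-offs for every possible final n in each cohort, under one stated criterion per cohort, with exact alpha and power beside each n, including n = 12.

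- **Cohort D.** The smallest cut-off with exact alpha of at most 0.12 keeps 3 of 12 and gives 2 for n = 5–6, 3 for n = 7–12 and 4 for n = 13–19. The 0.12 limit is chosen to preserve the printed rule; it is not in the plan. Holding the stated 0.10 would need 4 of 12 (0.026/0.507).
- **Cohort E.** The same 0.12 limit would move the printed 4 of 12 to 6 of 12 (0.054/0.613), cutting power from 0.927 to 0.613. Either state that change openly, or keep 4 of 12, restate its errors as 0.351/0.927, and name the criterion behind the rest of the table. Keeping the one-third proportion, rounded up, reproduces 4 of 12. Requiring power of at least 0.80 gives 5 of 12 (0.158/0.806) if the largest such cut-off is taken, so under that criterion 4 of 12 would have to be marked as an exception.

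The cost is a short table and an amended paragraph per cohort. Later freedom to choose is lost, and at most sizes the printed alpha or power will look less favourable than the figures now in the text.

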## **Brief Statistical Design**

Cohorts A and B: Randomized, double blinded, placebo-controlled, phase II design.

Cohorts C, D and E: Single stage, single arm, phase II design.

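### Cohort D: the rule of 3 or more of 12 has 75% power, not the stated 90%, and the quoted confidence interval fits no possible count out of 12

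*Combined protocol and SAP*

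**What the plan says.** Section 12.2, Cohort D, sets two reference rates. The active rate is given as: "We will consider a disease control rate (CR+PR+stable disease at 8 weeks) of 30% to be evidence of activity". The rate against which it is judged is worded: "in comparison to a disease control rate of 10% as not useful to pursue further".

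The decision rule and its claimed error rates follow: "For a 12-patient cohort with a type I error of 0.10 and a power of 0.90, if 2 or fewer patients have disease control", regorafenib is not taken further. On the other side, "If 3 or more patients have disease controlled at 8 weeks, regorafenib will be considered worthy of further investigation in Cohort D".

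On precision the same paragraph says: "A sample size of 12 patients will permit determination of disease control rate of 30% with 95% binomial confidence interval of (10%, 57" (the upper limit is a percentage).

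The final size is not fixed. Cohorts D and E share funding for 24 patients, and "the actual accrual will be used to define success vs failure for each cohort based on final accrual", with the 30% and 10% reference rates kept whatever the total. No cut-off is given for any size other than 12.

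The synopsis, under Brief Statistical Design, describes the design as: "Cohorts C, D and E: Single stage, single arm, phase II design".

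**The concern.** The paragraph gives everything needed to check it: the sample size, both rates, the cut-off and the claimed error rates. These do not fit together. Twelve patients are few for separating 10% from 30% at 90% power with a 10% type I error. The interval is also attached to a rate that 12 patients cannot produce.

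This is the cohort's go/no-go rule. Someone reading a negative result with the stated power in mind would think there was a 1 in 10 chance of having missed a drug that meets the target. If the true power is lower, that reading gives the negative result too much weight. The interval matters less, but it will be taken as the precision the cohort can deliver.

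**Working it through.** **Inputs** (all from section 12.2, Cohort D): n = 12; p0 = 0.10; p1 = 0.30; success if X ≥ 3; stated type I error 0.10; stated power 0.90; stated 95% interval 10% to 57%. The synopsis gives a single stage, so X is binomial(n, p).

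**1. The stated rule**

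P(X ≥ 3) = 1 − [(1−p)^12 + 12p(1−p)^11 + 66p²(1−p)^10]

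- At p = 0.30: 1 − (0.0138 + 0.0712 + 0.1678) = 1 − 0.2528 = **0.747** (stated 0.90).
- At p = 0.10: 1 − (0.2824 + 0.3766 + 0.2301) = 1 − 0.8891 = **0.111** (stated 0.10).

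The false-negative rate at the target is 1 − 0.747 = 0.253. A normal approximation at one-sided 0.10 gives power 0.749 and an arcsine approximation 0.693, so the choice of method does not explain the gap. The rule reaches 90% power only if the true rate is about 38.6%.

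**2. Other cut-offs at n = 12**

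| Success if | Type I error at 10% | Power at 30% |
|---|---|---|
| X ≥ 2 | 0.341 | 0.915 |
| X ≥ 3 | 0.111 | 0.747 |
| X ≥ 4 | 0.026 | 0.507 |

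None gives 0.10 with 0.90.

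**3. Other sample sizes.** A search over single-stage designs finds that the smallest with type I error ≤ 0.10 and power ≥ 0.90 is 5 or more of 25 (0.098, 0.910). Even if Cohort D took all 24 funded patients, 5 or more of 24 gives 0.085 and 0.889.

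**4. A two-stage origin.** The Simon optimal two-stage design for 10% versus 30% with both error rates at 0.10 computes to: stop if 1 or fewer of 12 respond, otherwise continue to 35 patients and fail at 5 or fewer (type I error 0.098, power 0.901). The stated 0.10 and 0.90 may come from such a design. That is inference, since the protocol mentions a Simon design only for Cohort E. Those error rates would belong to the full 35-patient trial, and its first-stage limit is 1 or fewer, not 2 or fewer.

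**5. The confidence interval.** 0.30 × 12 = 3.6 patients, which cannot be observed. Exact (Clopper-Pearson) 95% limits are:

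| Count | Rate | Lower | Upper |
|---|---|---|---|
| 3/12 | 25% | 5.5% | 57.2% |
| 4/12 | 33% | 9.9% | 65.1% |

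The quoted limits agree with the lower limit for 4/12 and the upper limit for 3/12. No whole-number count out of 12 gives 10% to 57% by the exact, Wilson, Jeffreys or Agresti-Coull method. Putting the fractional 3.6 into the formulas does not work either: exact 8.0% to 62.0%, Wilson 11.8% to 57.9%, Wald 4.1% to 55.9%.

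The exact method does reproduce the protocol's other two intervals: Cohort C, 15/30, 31% to 69%; Cohort E, 6/12, 21% to 79%.

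**The case against.** **The interval method is not named.** The plan says only that the interval is binomial. For 3/12 the Wilson interval is 8.9% to 53.2% (width 44 points) and the Jeffreys interval 7.6% to 52.9% (45 points). Both are narrower than the quoted 47 points. This stands: the claim that the quoted precision is too good holds only for exact intervals, whose widths are 52 points (3/12) and 55 points (4/12). It does not rescue the limits themselves, which no method tried yields for a count out of 12.

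**The sample size is approximate.** A Wilson interval for 3/11 is 9.7% to 56.6%, which rounds to the quoted figures. But the sentence is about 12 patients and a 30% rate, and 3/11 is 27%.

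**The type I error gap is small.** This also stands. The difference between 0.111 and 0.10 is about one point and comes from the discreteness of the binomial. The power is the substantive error.

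**Nothing in the conduct changes.** The rule at 12 patients is clear, numbers are limited by funding, and the cohort's primary objectives in section 1.1 are estimates. All true, and the correction leaves the rule as it is. But section 12.2 attaches a pass/fail conclusion to the rule, and the stated error rates determine how that conclusion is read.

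**Conclusion.** The statement is wrong as written. For success at 3 or more of 12, power at 30% is 0.747 against a stated 0.90, an overstatement of 15 points. The false-negative rate is 25%, two and a half times the 10% implied. The type I error is 0.111 rather than 0.10, a minor discrepancy. The stated pair cannot be met by any single-stage design within the 24 patients shared by Cohorts D and E.

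The interval of 10% to 57% is not the 95% interval for any count out of 12 by the methods tried, and the 30% rate it is attached to cannot occur.

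The error rates rest only on the plan's own inputs and on patients' outcomes being independent with a common rate. That the exact method was intended for the interval is inferred from its reproducing the Cohort C and Cohort E intervals.

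**What to change.** In section 12.2, Cohort D:

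1. Replace the stated error rates with the exact ones for 3 or more of 12: type I error 0.11, power 0.75.
2. Replace the interval with observable results, and name the method: exact 95% intervals of 5% to 57% for 3/12 (25%) and 10% to 65% for 4/12 (33%).
3. Preferably, because the final size may not be 12, set the cut-offs for other sizes now, together with the rule for choosing them. Exact values for 10% versus 30%:

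| n | Success if | Type I error | Power |
|---|---|---|---|
| 10 | ≥ 3 | 0.070 | 0.617 |
| 11 | ≥ 3 | 0.090 | 0.687 |
| 12 | ≥ 3 | 0.111 | 0.747 |
| 13 | ≥ 3 | 0.134 | 0.798 |
| 14 | ≥ 3 | 0.158 | 0.839 |
| 14 | ≥ 4 | 0.044 | 0.645 |
| 16 | ≥ 4 | 0.068 | 0.754 |
| 18 | ≥ 4 | 0.098 | 0.835 |

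The selection rule has to be explicit. A strict limit of 0.10 on type I error would require 4 or more at n = 12, with power 0.507. Keeping 3 or more means accepting 0.111. Sizes 13 and 14 need the same choice. Item 3 goes beyond the arithmetic correction, but it prevents a cut-off being chosen after the results are known.

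The cost is revised wording and a short table. No extra patients are needed and the rule at 12 is unchanged. The price is a less favourable power statement.

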### **Cohort E (Mesenchymal chondrosarcoma):**

Published estimates of progression free survival on chemotherapy for patients with metastatic mesenchymal chondrosarcoma patients are also unavailable. However, existing data indicate the overall survival of patients with metastatic mesenchymal chondrosarcoma is similar to those with unselected soft tissue sarcomas, in the 18 month range (Amer et al. J Orthop Res 2019, <https://doi.org/10.1002/jor.24463>), so we will estimate the RECIST 1.1 response rate (PR or better) at 24 weeks. Cohort E will accrue to ~ 12 patients with metastatic mesenchymal chondrosarcoma. We will consider a disease control rate (CR+PR+stable disease) at 24 weeks of 50% to be evidence of activity, as is the case with 1st line doxorubicin or gemcitabine in unselected STS (GEDDiS study) in comparison to a disease control rate of 25%, as not useful to pursue further.

A total of ~ 12 patients will be accrued to Cohort E,. Since funding is available for 24 patients in Cohorts D and E, the estimates of accruals, and the actual accrual will be used to define success vs failure for each cohort based on final accrual, maintaining similar disease control rates at 24 weeks (50% [active] vs 25% [not active]) for Cohort E, regardless of final accrual total.

The design is based on a Simon's two-stage using only the first stage. A 12-patient cohort with a type I error of 0.10 and a power of 0.80, yields a decision rule that if 3 or fewer patients have disease control at 24 weeks, then regorafenib will be determined to be unworthy of further study in this setting. If 4 or more patients have disease controlled at 24 weeks, regorafenib will be considered a worthy of further investigation in Cohort E. A sample size of 12 patients will permit determination of 24-week disease control rate of 50% with 95% binomial confidence interval of (21%, 79%).

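### Cohort E's go rule of 4 or more of 12 has an exact type I error of 0.35 and power of 0.93 at 25% versus 50%, not the stated 0.10 and 0.80

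*Combined protocol and SAP*

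**What the plan says.** Section 12.2 (Cohort E) fixes the two rates that the design must separate. For the active rate: "We will consider a disease control rate (CR+PR+stable disease) at 24 weeks of 50% to be evidence of activity". For the uninteresting rate: "in comparison to a disease control rate of 25%, as not useful to pursue further".

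It then gives the origin of the design, "The design is based on a Simon's two-stage using only the first stage", and attaches operating characteristics to it: "A 12-patient cohort with a type I error of 0.10 and a power of 0.80, yields a decision rule". The no-go boundary is 3 or fewer patients with disease control at 24 weeks. On the go side: "If 4 or more patients have disease controlled at 24 weeks, regorafenib will be considered a worthy of further investigation in Cohort E".

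The Synopsis confirms that there is no second stage. Its Brief Statistical Design reads "Cohorts C, D and E: Single stage, single arm, phase II design", and the entry on the maximum number of subjects also lists Cohort E as single stage with about 12 patients.

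The sample size is not fixed. Cohorts D and E share 24 funded places, and "The number of people studied in each group will vary according to the ability to accrue either diagnosis". Section 12.2 says that final accrual will define success or failure, "maintaining similar disease control rates at 24 weeks (50% [active] vs 25% [not active]) for Cohort E, regardless of final accrual total", but it gives no method for resetting the cut-off.

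**The concern.** Four of 12 is an observed rate of 33%, only one patient above the three expected if the true rate is 25%. A rule that passes so close to the null expectation cannot have a type I error near 0.10 at this sample size. The reference to a Simon first stage suggests how the figures may have arisen: a futility boundary may have been reused as a final go rule while the error rates of the full two-stage test were kept. The documents do not confirm this.

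This is the only decision rule stated for Cohort E, and there is no control arm to temper an over-reading. A reader who trusts the stated 0.10 would treat a pass at 4 or 5 of 12 as much stronger evidence than it is.

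**Working it through.** **Inputs**, all from section 12.2, Cohort E: n = 12; not-useful rate p0 = 0.25; active rate p1 = 0.50; go if X ≥ 4; stated type I error 0.10 and power 0.80.

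**Basis of calculation.** The section gives a 95% interval of 21% to 79% for a 50% rate in 12 patients. The exact (Clopper-Pearson) interval for 6/12 is 21.1% to 78.9%, so the plan's own interval is exact binomial. The same basis is used here.

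**Formula.** P(X ≥ c) = 1 − Σ C(12,k) p^k (1−p)^(12−k), summed over k = 0 to c−1.

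**Type I error of the stated rule (p = 0.25).** The terms for k = 0, 1, 2, 3 are 0.0317, 0.1267, 0.2323 and 0.2581, which sum to 0.6488. P(X ≥ 4) = 1 − 0.6488 = **0.351**, against 0.10 stated.

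**Power of the stated rule (p = 0.50).** P(X ≤ 3) = (1 + 12 + 66 + 220)/4096 = 299/4096 = 0.073. P(X ≥ 4) = **0.927**, against 0.80 stated.

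**Can another reading recover 0.10/0.80?**

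| Go at (of 12) | Type I error at 25% | Power at 50% |
|---|---|---|
| ≥ 3 | 0.609 | 0.981 |
| ≥ 4 (stated) | 0.351 | 0.927 |
| ≥ 5 | 0.158 | 0.806 |
| ≥ 6 | 0.054 | 0.613 |
| ≥ 7 | 0.014 | 0.387 |

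No row has type I error ≤ 0.10 and power ≥ 0.80. A normal approximation to the stated rule gives 0.252/0.876, or 0.369/0.926 with continuity correction, so it does not help. The smallest single-stage design meeting both targets is go at ≥ 8 of 19 (0.077/0.820).

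**The Simon route.** A first stage that stops at 3 or fewer of 12 does belong to complete designs meeting 0.10/0.80. Examples are go at ≥ 8 of 19 overall (0.074/0.807) and ≥ 8 of 20 (0.094/0.846). In those designs 4 or more of 12 means only that accrual continues; the later boundary brings the false-positive rate from 0.351 to below 0.10. Without a second stage, 0.351 is the final error.

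**Where the false passes fall.** At 25%, P(X = 4) = 0.1936 and P(X = 5) = 0.1032. Their share of all passes is (0.1936 + 0.1032)/0.3512 = 0.845. The exact 95% interval for 4/12 is 9.9% to 65.1%.

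**Sensitivity to the null rate.** The ≥ 4 rule passes 0.205 of the time at a true rate of 20% and 0.092 at 15%. The 0.351 is specific to the 25% that the plan specifies.

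**The case against.** The arithmetic is not open to dispute; the case on the other side is about how much it matters.

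- **Estimation, not testing.** The Cohort E primary objectives (section 1.1) are to estimate a PFS rate and a response rate at 24 weeks. The rule leads only to a view on further study, and no patient's treatment depends on it. This is true, but the go rule is still the cohort's only stated criterion, and its type I error is 3.5 times the figure given (0.351/0.10).
- **The rule errs towards leniency.** Power is understated, so fewer active drugs are discarded than claimed. A lenient screen in a rare tumour can be a legitimate choice. This stands, and is why keeping the rule is acceptable if its true properties are stated.
- **The truncation is disclosed.** The text says that only the first stage is used. However, the next sentence ties 0.10/0.80 to the 12-patient cohort, and a reader will take them as properties of this rule.
- **A second stage is speculative.** The documents show no planned second stage, final n or final boundary, and many complete designs share a 3/12 first stage. This stands: the two-stage designs above are illustrations, and a second stage is only one option.
- **Accrual is approximate.** It is, but the stated figures are explicitly for n = 12, and a floating n makes a stated resetting rule more necessary. At n = 12, holding type I error at 0.10 requires ≥ 6, holding power at 0.80 allows ≥ 5, and the text prints ≥ 4.

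**Conclusion.** The concern holds and must be fixed. At the plan's own rates, the 12-patient rule has a type I error of 0.351 and a power of 0.927. The stated 0.10 and 0.80 are both wrong for this rule, and no cut-off at n = 12 would make them right together. An agent with the uninteresting 25% rate passes about 35% of the time, and about 85% of those false passes are at exactly 4 or 5 of 12. A count of 6 or more would remain evidence of activity, since its probability at 25% is 0.054.

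The result assumes independent patients with a common disease control probability, exactly 12 patients in the denominator, and a final decision made on those 12 alone, as the Synopsis and section 12.2 describe.

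**What to change.** In section 12.2 (Cohort E), delete the 0.10/0.80 statement and print the exact properties of whichever rule is adopted.

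1. **Keep ≥ 4 of 12:** print type I error 0.35 and power 0.93, and describe the rule as a futility screen. This needs a few sentences and no extra patients; the cost is less favourable stated figures.
2. **Raise the cut-off:** ≥ 5 gives 0.16/0.81 and ≥ 6 gives 0.05/0.61. The false-negative rate at 50% rises from 7% to 19% or 39%.
3. **Add a second stage.** Keeping 3/12 and then requiring ≥ 8 of 19 (0.074/0.807) could need 7 more patients, which is 14 months at the 0.5 per month in section 12.3, and would leave 24 − 19 = 5 shared places for Cohort D. A different first stage is cheaper: stop at ≤ 2 of 9, otherwise go at ≥ 7 of 17 (0.098/0.806). Its maximum is 5 patients above 12, about 10 months, leaving 7 places.

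Keep the Simon sentence only under option 3.

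Under a single-stage rule, also choose one criterion for resetting the cut-off and print it before results are known. The plan gives no range for final n; 10 to 16 is assumed here. Entries are cut-off (type I error/power).

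| n | Type I error ≤ 0.10 | Power ≥ 0.80 (highest cut-off that keeps it) |
|---|---|---|
| 10 | ≥ 5 (0.078/0.623) | ≥ 4 (0.224/0.828) |
| 11 | ≥ 6 (0.034/0.500) | ≥ 4 (0.287/0.887) |
| 12 | ≥ 6 (0.054/0.613) | ≥ 5 (0.158/0.806) |
| 13 | ≥ 6 (0.080/0.709) | ≥ 5 (0.206/0.867) |
| 14 | ≥ 7 (0.038/0.605) | ≥ 5 (0.258/0.910) |
| 15 | ≥ 7 (0.057/0.696) | ≥ 6 (0.148/0.849) |
| 16 | ≥ 7 (0.080/0.773) | ≥ 6 (0.190/0.895) |
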